3.0 OVERVIEW OF CLINICAL TRIAL

3.1 Study Objectives

3.1.1 Primary Objectives

Measure the effect of endocrine targeted therapy on ER expression and estradiol binding to the receptor using serial FES PET and FDG PET.

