2.2 Background

This single-site study will investigate the ability of [18F]FES to quantify changes in ER expression and estradiol binding in vivo in patients with breast cancer for whom endocrine-targeted therapy has been chosen based on clinical presentation or as part of therapeutic clinical trial. The results of this trial will help evaluate the effect of ER-directed therapies on ER expression and estrogen binding to ER, and secondarily whether the FES PET measures of estrogen receptor function, and changes with treatment, predict response to endocrine targeted therapy in patients with known ER+ primary or metastatic breast cancer as measured by immunohistochemistry (IHC) of biopsy material. The primary goal is to gain insight into the efficacy of ER-targeted therapies, especially novel therapies, on ER expression and estrogen binding to ER. For example, serial FES PET imaging could be used to test the efficacy of an ER antagonist in blocking estradiol binding, or the ability of an agent directed at altering ER expression to change ER expression levels in tumors. Such in vivo measures of the pharmacodynamics of ER-directed therapy have traditionally required serial biopsy and have been quite challenging. FES PET presents a non-invasive alternative to measure the effects of ER-directed therapy.

Invasive breast carcinoma: Each year, invasive breast cancer will be diagnosed in over 250,000 women and account for over 40,000 deaths in the United States (1). Advances in diagnosis and therapy have resulted in increased survival for early breast cancer (1-3). This increase in breast cancer survival may result in more patients diagnosed with advanced or metastatic breast cancer. Individualized medicine tailoring therapy to patients shows promise to care for this disease (4).

Invasive breast carcinoma and hormone receptors: The incidence of hormone receptor positive disease is approximately 79% (1, 2). Physicians generally choose endocrine-targeted therapies as first-line treatments for patients with ER+ advanced disease due to improved tolerability as well as ease of administration. Nonetheless, chemotherapy is frequently offered to patients without proof of superior outcomes. Measurement of tumor hormone receptor expression, both estrogen receptor (ER) and progesterone receptor (PgR) at the time of primary diagnosis is standard of clinical care (5). Knowledge of hormone receptor

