In prior observational imaging trials (unpublished data): we have measured regional estrogen-ER binding using FES PET before and after treatment with estrogen depleting therapies, Aromatase inhibitors (AI), and estrogen blocking therapies, Tamoxifen (TAM), or fulvestrant (FUL) in 30 metastatic breast cancer patients. As expected, tumor FES uptake declined markedly on ER blockers TAM and FUL (average 54% decline), but less than 15% on average on estrogen-depleting AIs ($p < 0.001$). All 5/5 patients

[figure not shown]
taking TAM showed complete tumor blockade (FES SUV \leq 1.5 after treatment), compared to 4/11 of FUL patients ($p=0.009$). Other studies have also shown that FES PET can measure estrogen receptor suppression (16). We concluded that molecular imaging can assess the in vivo pharmacodynamics of targeted agents, and may give insight into the activity of established therapeutic agents.

Phase II trial: Twenty-three patients with ER+/HER2- metastatic breast cancer with prior clinical benefit from endocrine therapy but later progression on aromatase inhibitor (AI) therapy were included in a Phase II trial of vorinostat to restore endocrine sensitivity in ER+/HER2- metastatic breast cancer, with molecular imaging correlates. 18F-FES PET and 18F-Fluorodeoxyglucose (18F-FDG) PET scans were performed at baseline, week 2, and week 8. Simultaneous HDACi and AI dosing in patients with cancers resistant to AI alone was promising with clinical benefit (6+ months without progression) in 4 of 10 evaluable patients. Higher 18F-FES-PET uptake identified patients likely to benefit from combination therapy, but vorinostat did not appear to change ER expression (results submitted for publication).

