3.3 Study Design

This clinical study will investigate the utility of [18F]FES in patients with estrogen receptor (ER) positive, primary, recurrent or metastatic, breast carcinoma. [18F]FES PET has been validated as a measure of estrogen receptor expression. This trial is also designed to test the safety of [18F]FES. In addition, this study will obtain data on the value of [18F]FES to predict and evaluate response to endocrine-targeted therapies as a measure of ER expression in this patient population. If promising, these data will be used to design a phase II multi-center clinical trial.

We anticipate that the imaging measure of receptor density will predict the likelihood that a patient will respond to hormone targeted therapy, evaluate subsequent changes in this measure as the patient undergoes therapy and that eventually [18F]FES imaging will help us design therapeutic trials for better treatment outcomes. We also expect that repeat [18F]FES PET imaging shortly after the start of endocrine-targeted therapy will reflect the pharmacodynamics of endocrine targeted therapy.

Briefly, patients with primary, recurrent or metastatic breast cancer from an ER+ primary tumor who will be undergoing endocrine-targeted therapy will be imaged with [F-18]-16 α -fluoroestradiol. All patients will undergo a pre-therapy FES PET or FES PET/CT scan (hereafter FES PET will be used to denote both FES PET and FES PET/CT unless specifically noted). In some patients receiving non-interfering medications such as aromatase inhibitors, scans may be performed with patients already on a treatment who are to start an alternative or additional endocrine targeted treatment. Patients will undergo a repeat FES PET and FDG PET on study after starting the endocrine-targeted therapy. The exact timing of the repeat scans may vary depending on the treatment regimen. In the repeat studies, we will be testing the ability of FES PET and FDG PET to measure the pharmacologic effect of endocrine-targeted therapy and early measures that may help predict response to such targeted agents. In patients on selective estrogen receptor degrader (SERD) therapies, where repeat FES PET is used primarily to evaluate residual ER availability rather than tumor response, repeat FDG PET may be omitted, as determined by requirements of the co-enrolling companion therapeutic protocol. A subset of patients may undergo a third FES PET at a later time point determined by the treatment regimen.

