We emphasize that this is an observational study in that [18F]FES PET will not be used to direct therapy. Treatment regimens are chosen by the referring oncologist prior to the [18F]FES PET study on the basis of clinical criteria or participation in experimental treatment protocols. While patients and referring physicians will not be blinded to [18F]FES PET results, treatment choices will be made prior to the entry of the patient into the study and will not be altered because of the FES PET results.

Patients with metastatic or recurrent disease may consent to optional research biopsies performed prior to start of the selected endocrine-targeted therapy, and after 1-12 weeks on therapy. Obtained tissues will be analyzed for expression of prognostic markers and/or for intra-tumor steroid hormone concentrations to evaluate correlations between results of imaging and histo-pathological studies and to enhance understanding of mechanisms of response and resistance in the context of tumor microenvironment.

Below is an outline for this schema:

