3.3.1 Primary Endpoint

The primary endpoints will be quantitative and qualitative measures of FES uptake, and measures of change in FES uptake between pre-therapy and post-therapy scans

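### For drugs that bind the oestrogen receptor, change in FES uptake alone cannot support the ER-expression half of the primary objective

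*Combined protocol and SAP*

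**What the plan says.** Section 3.1.1 gives one primary objective: "Measure the effect of endocrine targeted therapy on ER expression and estradiol binding to the receptor using serial FES PET and FDG PET". Section 8.1 (Treatment Plan Overview) gives the same two targets as the purpose of the second FES and FDG scans. The primary endpoint in section 3.3.1, repeated in section 17.0, is uptake itself and "measures of change in FES uptake between pre-therapy and post-therapy scans". The expected primary analysis in section 17.0 is a one-sample test of the average percent change in FES SUV, with no split by type of drug.

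Elsewhere the protocol treats blockade and expression as different things. Section 2.2 says serial FES could test whether an antagonist blocks estradiol binding, "or the ability of an agent directed at altering ER expression to change ER expression levels in tumors". Section 2.2.2 reports that "tumor FES uptake declined markedly on ER blockers TAM and FUL (average 54% decline), but less than 15% on average on estrogen-depleting AIs", and that all 5 of 5 patients "taking TAM showed complete tumor blockade", against 4 of 11 on fulvestrant. For SERDs, section 3.3 says that "repeat FES PET is used primarily to evaluate residual ER availability rather than tumor response". The same section also describes FES PET as validated for measuring ER expression and does not limit that to scans taken off ER-binding drugs.

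ER is measured directly on treatment only by IHC on research biopsies (section 14.0, Biologic Correlates). Patients with metastatic or recurrent disease "may consent to optional research biopsies performed prior to start of the selected endocrine-targeted therapy" and again on therapy. The results feed a secondary correlation in section 3.1.2, to be done where relevant to the regimen.

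**The concern.** The objective names two effects and the endpoint is one number. For a drug that sits on the receptor, that number can move through either effect. Section 6.1 recognises this for the baseline scan by requiring at least 6 weeks off ER blockers. The same condition cannot hold at the repeat scan when the regimen under study is itself an ER blocker.

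At stake is what a positive result may be said to show. A clear fall in FES on a SERM or SERD would meet the planned test, and the objective as worded would let it be read as an effect on ER expression. For a degrader, whether receptor is lost or only blocked is the question of interest. Section 3.3 says that promising results will be used to design a phase II multi-center trial, so an unsupported reading could carry forward.

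**Working it through.** **1. The plan's own figures.** Inputs from section 17.0: n = 20, SD 25 percentage points (30 as a variant), level 0.05. Normal approximation: power = Φ(δ/SD × √n − z), where δ is the distance of the true change from the null value.

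- One-sided against 20%, true 40%: Φ(20/25 × 4.472 − 1.645) = 0.973 (stated 0.97).
- One-sided against 20%, true 35%: Φ(15/25 × 4.472 − 1.645) = 0.85 (stated 0.85).
- Two-sided against zero, true 20%: Φ(20/25 × 4.472 − 1.960) = 0.947 (stated 0.95).
- The same with SD 30: Φ(20/30 × 4.472 − 1.960) = 0.847 (stated 0.85).

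The figures reproduce. An exact t calculation gives 0.964, 0.827, 0.924 and 0.807. All of them concern change in FES SUV and say nothing about which effect produced the change.

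**2. The passages side by side.** The objective (3.1.1, 8.1) claims expression and binding. The endpoint and analysis (3.3.1, 17.0) use FES change only. The background data (2.2.2) label the tamoxifen fall blockade. The SERD paragraph (3.3) reads repeat FES as residual availability. No section says which construct a fall supports for which drug class. A literal expression reading would also make tamoxifen (5/5 at SUV 1.5 or below) look like a stronger remover of receptor than fulvestrant (4/11), which section 2.2 calls a down-modulator. The protocol does not draw that conclusion, but nothing in the objective prevents it.

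**3. How wide the ambiguity is, under an assumed model.** Assume uptake is proportional to R × (1 − θ). R is receptor amount relative to baseline, and θ is the fraction newly occupied by the drug. The documents do not state this model. A 54% mean fall gives 1 − 0.54 = 0.46 = R × (1 − θ).

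- θ = 0: R = 0.46, a 54% loss of receptor.
- θ = 0.25: R = 0.46/0.75 = 0.61, a 39% loss.
- θ = 0.54: R = 0.46/0.46 = 1.00, no loss.

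One equation with two unknowns stays unresolved at any sample size.

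**4. What the planned test would do.** Suppose receptor amount is unchanged and the 54% fall is all occupancy. With SD 25, the one-sided t-test against 20% is positive with probability 0.80 at n = 5, 0.99 at n = 10 and above 0.999 at n = 20. A positive test is therefore close to certain with no expression effect at all.

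**5. Pooling mechanisms.** Take blockers at 54% and aromatase inhibitors at 15% (the upper bound of the reported figure), n = 20, SD 25 within each group. With 25%, 50% and 75% of patients on blockers the mean falls are 24.75%, 34.5% and 44.25%. The same test is positive with probability about 0.12, 0.65 and 0.98 (100,000 simulated trials each). With aromatase inhibitors only it is 0.006. The pooled result would depend heavily on the drug mix, which the plan does not fix.

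**The case against.** The best defence is that the documents already keep the two constructs apart. Binding is named in the objective. Section 2.2 pairs antagonists with blocked binding and expression-altering agents with changed expression. Section 2.2.2 speaks of expression and/or blockade, and no passage reads a fall on a blocker as lost receptor. Patients come from varied companion studies, some with no ER-binding drug. In the vorinostat plus aromatase inhibitor trial, for example, an expression reading was used. The endpoint is worded neutrally as change in uptake. Paired same-site biopsies exist for a subset, and making them optional is reasonable in a pilot of about 20.

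Much of this stands. The estradiol-binding half is sound, the endpoint needs no rewording, and no stated rule turns a fall in FES into a claim of receptor loss. What does not stand is the idea that naming both constructs settles the matter. Sections 3.1.1 and 8.1 still list expression as an outcome of serial FES for every regimen, the analysis averages over mechanisms, and the only direct check is optional and secondary.

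A reader might infer something stronger: that FES falls on these drugs with no loss of receptor. The documents do not support that. They give no on-treatment receptor counts, and the 54% pools tamoxifen with fulvestrant, whose fall may mix occupancy and loss. The supported statement is that FES can fall without receptor loss and that the two cannot be separated.

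**Conclusion.** The point holds in a limited form. For SERMs, SERDs and other ER-binding drugs, the planned mean change in FES cannot by itself support a conclusion on ER expression, and nothing in the primary analysis separates occupancy from loss. This rests on the protocol's own text, not on the model.

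The 0% to 54% range is an illustration. It depends on proportional uptake and takes receptor amount not to rise and occupancy not to fall below baseline. It also ignores other influences on uptake, such as metabolites and binding globulin, which section 2.2.1 mentions. The probabilities in steps 4 and 5 add the protocol's SD of 25 and the stated mean falls.

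Two further inferences should be resisted. The primary objective as a whole does not fail, since FES change does address estradiol binding. Nor does the argument apply in the same way to non-ER-binding regimens such as aromatase inhibitors, although there too a change in endogenous estradiol may alter occupancy. The change is worth making before analysis because it limits what the trial may conclude. The power figures are unaffected.

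**What to change.** - Keep the endpoint in sections 3.3.1 and 17.0 as observed change in FES SUV.
- Reword section 3.1.1, and the matching sentence on the repeat scans in section 8.1, as the effect of therapy on ER available for estradiol binding.
- In section 17.0, report FES change by drug mechanism: ER blocker, SERD, non-ER-binding.
- State that for ER-binding regimens no conclusion on ER expression is drawn from FES alone. Present expression there only from paired same-site biopsy IHC in consenting patients, as supportive evidence, because the Allred score is semi-quantitative.
- For non-ER-binding regimens, allow an expression reading with the caveat on endogenous estradiol, using serum estradiol and SHBG where collected.

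Scans, visits, biopsies and sample size do not change. The costs are a narrower primary claim and small groups: 20 patients over three mechanisms is under 7 each on average, so the breakdown would be descriptive.

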3.1.2 Secondary Objectives

Document the safety profile of FES PET in patients with breast cancer.

Examine associations between FES PET results and serial measurements of hormone or other levels in peripheral blood, as related to efficacy of endocrine-targeted therapy. Correlate FES PET uptake measures with histopathological assays and tumor microenvironment studies on biopsy specimens, if relevant to specific treatment regimen.

3.2 Study Population

This study focuses on patients with estrogen receptor (ER) positive, primary, recurrent or metastatic, breast carcinoma. Further detail on the subject population can be found in the inclusion and exclusion criteria listed under section 7.

The population for this study will be recruited from patient rosters in other studies that require a FES scan as a research procedure.

3.3 Study Design

This clinical study will investigate the utility of [18F]FES in patients with estrogen receptor (ER) positive, primary, recurrent or metastatic, breast carcinoma. [18F]FES PET has been validated as a measure of estrogen receptor expression. This trial is also designed to test the safety of [18F]FES. In addition, this study will obtain data on the value of [18F]FES to predict and evaluate response to endocrine-targeted therapies as a measure of ER expression in this patient population. If promising, these data will be used to design a phase II multi-center clinical trial.

We anticipate that the imaging measure of receptor density will predict the likelihood that a patient will respond to hormone targeted therapy, evaluate subsequent changes in this measure as the patient undergoes therapy and that eventually [18F]FES imaging will help us design therapeutic trials for better treatment outcomes. We also expect that repeat [18F]FES PET imaging shortly after the start of endocrine-targeted therapy will reflect the pharmacodynamics of endocrine targeted therapy.

Briefly, patients with primary, recurrent or metastatic breast cancer from an ER+ primary tumor who will be undergoing endocrine-targeted therapy will be imaged with [F-18]-16 α -fluoroestradiol. All patients will undergo a pre-therapy FES PET or FES PET/CT scan (hereafter FES PET will be used to denote both FES PET and FES PET/CT unless specifically noted). In some patients receiving non-interfering medications such as aromatase inhibitors, scans may be performed with patients already on a treatment who are to start an alternative or additional endocrine targeted treatment. Patients will undergo a repeat FES PET and FDG PET on study after starting the endocrine-targeted therapy. The exact timing of the repeat scans may vary depending on the treatment regimen. In the repeat studies, we will be testing the ability of FES PET and FDG PET to measure the pharmacologic effect of endocrine-targeted therapy and early measures that may help predict response to such targeted agents. In patients on selective estrogen receptor degrader (SERD) therapies, where repeat FES PET is used primarily to evaluate residual ER availability rather than tumor response, repeat FDG PET may be omitted, as determined by requirements of the co-enrolling companion therapeutic protocol. A subset of patients may undergo a third FES PET at a later time point determined by the treatment regimen.

FDG PET and CT will be used as staging tests for this study and FDG will also serve as a comparator for tumor localization with the FES imaging. Patients will have a clinical FDG PET scan prior to the start of treatment as part of their standard care; their treating physician will order this. In rare cases where an FDG PET has recently been performed at an outside medical facility but the scan has inadequate image quality or insufficient quantitative information, or for patients who would not be ordered as a standard part of the patient's care, a baseline FDG scan will be done as part of this protocol. A second FDG PET scan will be done as a study procedure concurrent with the FES PET timing stipulated by treatment regimen (this may vary from 1 to 12 weeks post treatment start depending on regimen). In the subset of patients undergoing a third FES PET scan there may also be a research FDG PET done at the same time point if indicated by the treatment regimen.

After the FES and FDG baseline imaging (see schematic below), the patients will start or change therapy, typically within 30 days, and be followed clinically for up to 20 years. Lesion location will be identified using clinical FDG scans with reference to clinical CT for metastatic disease or ultrasound, mammography, and/or breast MRI for primary tumors in patients presenting with metastatic or recurrent disease that still have a primary breast lesion. FES and FDG images will be spatially co-registered and tumor regions will be drawn on the FDG images and transferred to the FES images for quantitative analysis of FES uptake in both ER positive and ER negative tumors. For FDG studies, SUVs will be generated.

[figure not shown]
The FES uptake from images will be analyzed qualitatively by visual assessment and quantitatively using a standard uptake value (SUV). Serial measurements of hormone levels in peripheral blood may be used with some treatment regimens to allow determination of efficacy of endocrine therapy. ER, PR and HER2 assays will allow determination of hormone receptor status and

whether HER2 over-expression indicates estrogen-independent growth in some treatment studies, however, there may not be pathologic correlates in all studies.

We emphasize that this is an observational study in that [18F]FES PET will not be used to direct therapy. Treatment regimens are chosen by the referring oncologist prior to the [18F]FES PET study on the basis of clinical criteria or participation in experimental treatment protocols. While patients and referring physicians will not be blinded to [18F]FES PET results, treatment choices will be made prior to the entry of the patient into the study and will not be altered because of the FES PET results.

Patients with metastatic or recurrent disease may consent to optional research biopsies performed prior to start of the selected endocrine-targeted therapy, and after 1-12 weeks on therapy. Obtained tissues will be analyzed for expression of prognostic markers and/or for intra-tumor steroid hormone concentrations to evaluate correlations between results of imaging and histo-pathological studies and to enhance understanding of mechanisms of response and resistance in the context of tumor microenvironment.

Below is an outline for this schema:

